1. REPORTING & ANALYSIS PLAN SYNOPSIS

Overview	Key Elements of the RAP
Purpose	The purpose of this reporting and analysis plan (RAP) is to describe: 
 Planned analyses and output for the final data.
Protocol	
 This RAP is based on Protocol Amendment 1(Dated: 05/JAN/2017) of study 202062 (GlaxoSmithKline Document Number 2016N288743_01)
Primary Objective	
 To assess the safety and tolerability of single and repeat doses of GSK2292767 as a dry powder in healthy cigarette smokers.
Primary Endpoint	
 Safety and tolerability of GSK2292767 as assessed by clinical monitoring of: 
 Vital Signs Spirometry Electrocardiogram (ECG) Laboratory safety data Adverse events (AEs)
Study Design	
 This is a two part, single site, randomised, double-blind (sponsor open), placebo controlled study in healthy smokers. Part A will consist of two 3-period interlocking cohorts. Part B is planned to follow Part A and is a parallel group design. The highest well tolerated dose achieved in Part A will be selected for Part B.
Planned Analyses	
 All decisions regarding final analysis, as defined in this RAP document, will be made prior to Database Freeze (unblinding) of the study data.
Primary Analysis Population	
 Primary: Safety Population (Comprised of subjects who receive at least one dose of study treatment and will be based on the treatment which the subject actually received).
Estimation	
 An estimation and inference approach will be adopted to evaluate the objectives.
Primary Analyses	
 Safety data will be presented in tabular and/or graphical format and summarised descriptively according to GSK's Integrated Data Standards Library (IDSL) standards.
Secondary Analyses	
 Pharmacokinetic: Individual GSK2292767 plasma concentration-time profiles (by treatment and subject) and median/mean (\pmSD) profiles by treatment group will be plotted. Plasma concentration time data for GSK2292767 will be analyzed by non-compartmental methods using WinNonlin and derived PK parameters will be graphically presented, summarised and listed. Data will be analysed for dose proportionality and dose accumulation, peak to trough ratio and steady state. Pharmacodynamic: All endpoints will be presented in graphical format and/or summarised descriptively and listed.

2. SUMMARY OF KEY PROTOCOL INFORMATION

2.1. Changes to the Protocol Defined Statistical Analysis Plan

One of the protocol defined endpoints was:

Semi quantitative characterisation of intracellular distribution of GSK2292767 within lung resident cells, binding and lysosomal uptake and retention.

Unfortunately, this binding and lysosomal work failed during preliminary investigation and so only the imaging of the cell for drug will be investigated, though it is uncertain whether the compound ionises sufficiently to allow detection.

2.2. Study Objective(s) and Endpoint(s)

Objectives	Endpoints
Primary Objectives	Primary Endpoints

 To assess the safety and tolerability of single and repeat doses of GSK2292767 as a dry powder in healthy cigarette smokers. 	Safety and tolerability of GSK2292767 as assessed by clinical monitoring of: 
 Vital Signs Spirometry ECG Laboratory safety data Adverse events (AEs)
Secondary Objectives	Secondary Endpoints

 To determine the pharmacokinetic profile of single and repeat doses of GSK2292767 as a dry powder in healthy cigarette smokers 	
 GSK2292767 plasma concentration data and derived pharmacokinetic parameters including area under the plasma drug concentration versus time curve ($AUC_{(0-t)}$, $AUC_{(0-24)}$, $AUC_{(0-\infty)}$), maximum observed plasma drug concentration (C_{max}), time to maximum observed plasma drug concentration (T_{max}), terminal half-life ($T_{1/2}$) and trough concentrations (C_{τ}) following single and repeated dry powder doses, where data allow.

 To investigate the steady-state trough concentration of GSK2292767 in lung epithelial lining fluid (ELF) and Bronchoalveolar lavage (BAL) cell pellet after repeat inhaled dry powder administration in healthy cigarette smokers. 	
 BAL concentrations of GSK2292767 and derived lung ELF and cell pellet deposition parameters.

Objectives	Endpoints
Exploratory Objectives	Exploratory Endpoints

 To determine the pharmacodynamic effect of GSK2292767 on the biomarker Phosphatidylinositol (3,4,5)-trisphosphate (PIP3) in induced sputum after single and repeat doses of GSK2292767 administered as a dry powder in healthy cigarette smokers. 	
 PIP3 peak area as a proportion of (PIP3 peak area + Phosphatidylinositol (4,5)-bisphosphate [PIP2] peak area) in induced sputum cells.

 To explore the intracellular distribution, binding and lysosomal disposition of GSK2292767 from lung resident cells derived from bronchoalveolar lavage at steady-state following repeat administration 	
 Semi quantitative characterisation of intracellular distribution of GSK2292767 within lung resident cells, binding and lysosomal uptake and retention.

 To generate samples that will be used to characterise the metabolic profile of GSK2292767 in plasma, following single and repeat doses of GSK2292767 administered as a dry powder in healthy cigarette smokers. 	
 Characterisation and quantification of metabolites in plasma.

 To collect urine samples only at the highest proposed dose level to characterise the renal excretion of systemically available drug following inhaled delivery. 	
 Semi-quantitative characterisation of amount of parent GSK2292767 excreted in urine

3. PLANNED ANALYSES

3.1. Interim Analyses

No formal statistical analysis is planned.

A review of preliminary safety and pharmacokinetic data will be conducted prior to selection of the doses for Part A and before confirmation of the dose for Part B. Safety data will be provided by the site at the end of each dosing session. Pharmacokinetic data will be provided by or under the auspices of Clinical Pharmacokinetics Modelling & Simulation (CPMS) using Phoenix WinNonlin.

The decision to proceed to the next dose level of GSK2292767 in Part A and the selection of the daily dose level to be tested in Part B will be made by the GSK Study Team and the investigator based on blinded safety data (AE, vital signs, ECG and laboratory safety test) and preliminary blinded PK data (up to 24 h) obtained in at least 5 subjects on active

drug at the previous dose level. For a detailed description of the dose justification please refer to protocol Section 10.3.4.

3.2. Final Analyses

The final planned primary analyses will be performed after the completion of the following sequential steps:

1. All subjects from both study parts have completed the study as defined in the protocol.
2. All required database cleaning activities have been completed and final database release and database freeze has been declared by Data Management.
3. All criteria for unblinding the randomisation codes have been met.
4. Randomisation codes have been distributed according to RandAll NG procedures.

4. ANALYSIS POPULATIONS

Population	Definition / Criteria	Analyses Evaluated
Screened	
 • Comprise of all subjects who were screened 	
 • Listings
Safety	
 • Comprise of all subjects who receive at least one dose of study treatment. • This population will be based on the treatment the subject actually received. 	
 • Study Population • Safety • Pharmacodynamic
Pharmacokinetic	
 • Subjects in the 'Safety' population for whom a pharmacokinetic sample was obtained and analysed. • This population will be based on the treatment the subject actually received. 	
 • PK

NOTES :

Please refer to [Appendix 11](#): List of Data Displays which details the population to be used for each displays being generated.

4.1. Protocol Deviations

- Important protocol deviations (including deviations related to study inclusion/exclusion criteria, conduct of the trial, patient management or patient assessment) will be summarised and listed.
- Protocol deviations will be tracked by the study team throughout the conduct of the study in accordance with the Protocol Deviation Management Plan.
- A separate summary and listing of all inclusion/exclusion criteria deviations will also be provided. This summary will be based on data as recorded on the inclusion/exclusion page of the eCRF.

5. HANDLING CONVENTIONS

[Table 1](#) provides an overview of appendices within the RAP for outlining general considerations for data analyses and data handling conventions.

Table 1 Overview of Appendices

Section	Component
Section 10.1	Appendix 1: Time & Events
Section 10.2	Appendix 2: Assessment Windows
Section 10.3	Appendix 3: Treatment States and Phases
Section 10.4	Appendix 4: Data Display Standards & Handling Conventions
Section 10.5	Appendix 5: Derived and Transformed Data
Section 10.6	Appendix 6: Premature Withdrawals & Handling of Missing Data
Section 10.7	Appendix 7: Values of Potential Clinical Importance
Section 10.8	Appendix 8: Model Checking and Diagnostics for Statistical Analyses.
Section 10.9	Appendix 9: Population Pharmacokinetic Analyses
Section 10.10	Appendix 10: Abbreviations and Trademarks
Section 10.11	Appendix 11: List of Data Displays

6. STUDY POPULATION ANALYSES

6.1. Overview of Planned Analyses

The study population analyses will be based on the “Safety” population, unless otherwise specified.

[Table 2](#) provides an overview of the planned study population analyses, with full details of data displays being presented in [Appendix 11: List of Data Displays](#).

Table 2 Overview of Planned Study Population Analyses

Display Type	Data Displays Generated		
	Figure	Table	Listing
Randomisation			
Randomisation			Y
Subject Disposition			
Subject Disposition		Y	
Reasons for Screening Failures			Y
Important Protocol Deviations		Y	Y
Inclusion and Exclusion Criteria Deviations		Y	Y
Demography			
Demographics Characteristics		Y	Y
Race & Racial Combinations		Y	Y
Study Populations		Y	Y
Medical Condition & Concomitant Medications			
Medical Conditions (Current/Past)		Y	
Concomitant Medication		Y	

NOTES:

- Y = Yes display generated.

7. PRIMARY STATISTICAL ANALYSES**7.1. Safety Analyses****7.1.1. Overview of Planned Safety Analyses**

The safety analyses will be based on the Safety population, unless otherwise specified.

7.1.2. During the Study

As required, ongoing data reviews will be conducted by the study team of the unblinded safety data, throughout the trial progression.

7.1.2.1. Dose Escalations

- The principal investigator and medical monitor will provide an overall summary of the required safety data for the dose escalation review for progressing to the next cohort, as defined in the protocol.

7.1.3. Final Safety Data

Table 3 provides an overview of the planned safety analyses, with full details of data displays being presented in Appendix 11: List of Data Displays.

Table 3 Overview of Planned Safety Analyses

Endpoint / Parameter/ Display Type	Absolute				Change from Baseline			
	Summary		Individual		Summary		Individual	
	T	F	F	L	T	F	F	L
Exposure								
Extent of Exposure	Y			Y				
Adverse Events								
All AEs (Safety population)	Y			Y				
Drug-related AEs	Y							
Serious AEs				Y				
AEs leading to withdrawal				Y				
Relationship between SOC and verbatim text				Y				
AEs by Preferred Term with Occurrences >=5% in any treatment arm	Y							
Laboratory Data								
Clinical Chemistry				Y ¹	Y			
Haematology				Y ¹	Y			
Urinalysis Data				Y ¹	Y			
ECG								
ECG Values		Y	Y	Y ²	Y			
ECG Findings	Y			Y				
Frequency of Maximum ECG Values by Pre-Specified Categories	Y							
Vital Signs								
Vital Signs Values				Y ³	Y			
Spirometry								
Lung Function Parameters				Y	Y			

NOTES:

- T = Table, F = Figures, L = Listings, Y = Yes display generated, SOC = System Organ Class, PT = Preferred Term.
- Summary = Represents TF related to any summaries (i.e. descriptive statistics) of the observed raw data.
- Individual = Represents FL related to any displays of individual subject observed raw data.

[1]Two Listings of chemistry and haematology data will be produced. One will list all abnormalities of PCI and the other will list all chemistry/haematology data for all subjects with any chemistry/haematology abnormalities.

[2]Two listings of ECG data will be produced. One will list all ECG abnormalities of PCI and the other will list all ECG data for all subjects with any ECG PCI values.

[3]Two listings of vital signs data will be produced. One will list all vital signs abnormalities of PCI and the other will list all vital signs data for all subjects with any vital signs PCI values.

8. SECONDARY STATISTICAL ANALYSES

8.1. Pharmacokinetic Analyses

8.1.1. Overview of Planned Pharmacokinetic Analyses

The following PK analyses will only be performed if sufficient data are available (i.e., if subjects have well defined plasma profiles). Analyses will be performed on the Pharmacokinetic Population.

8.1.2. Drug Concentration Measures

Refer to [Appendix 4: Data Display Standards & Handling Conventions](#) (Section [10.4.3 Reporting Process & Standards](#)).

8.1.2.1. Overview of Planned Pharmacokinetic Analyses for Drug Concentrations

[Table 4](#) provides an overview of the planned pharmacokinetic analyses, with further details of data displays being presented in [Appendix 11: List of Data Displays](#).

Table 4 Overview of Planned Pharmacokinetic Data

Endpoints	Untransformed				Log-Transformed			
	Summary		Individual		Summary		Individual	
	F	T	F	L	F	T	F	L
Plasma Drug Concentrations	Y ^[1] _[2]	Y	Y ^[1]	Y		Y	Y	
Derived PK Parameters		Y		Y		Y		
Urine PK Data		Y						
Lung ELF and Cell Pellet	Y	Y					Y	

NOTES:

- T = Table, F = Figures, L = Listings, Y = Yes display generated.
 - Summary = Represents TFL related to any summaries (descriptive statistics) of the observed raw data.
 - Individual = Represents FL related to any displays of individual subject observed raw data.
1. Linear and Semi-Log plots will be created on the same display.
 2. Median plots will be generated.

8.1.3. Pharmacokinetic Parameters

8.1.3.1. Deriving Pharmacokinetic Parameters

- Refer to [Appendix 4: Data Display Standards & Handling Conventions](#) (Section [10.4.3 Reporting Process & Standards](#)).
- The pharmacokinetic parameters will be calculated by standard non-compartmental analysis according to current working practices and using Nonlin Pro.
- All calculations of non-compartmental parameters will be based on actual sampling times recorded during the study.

- Pharmacokinetic parameters described in [Table 5](#) will be determined from plasma GSK2292767 concentration-time data, as data permit.

Table 5 Derived Pharmacokinetic Parameters

Parameter	Parameter Description
AUC(0-t)	Area under the concentration-time curve from time zero to the time of the last quantifiable concentration (C(t)) will be calculated using the linear trapezoidal rule for each incremental trapezoid and the log trapezoidal rule for each decremental trapezoid.
AUC(0-24)	Area under the concentration-time curve over the dosing interval.
AUC(0-∞)	Area under the concentration-time curve extrapolated to infinity will be calculated as follows: AUC = AUC(0-t) + C(t)/λ _z .
C _{max}	Maximum observed concentration, determined directly from the concentration-time data.
C _τ	Trough concentration
T _{max}	Time to reach C _{max} , determined directly from the concentration-time data.
T _{1/2}	Apparent terminal half-life will be calculated as: $t_{1/2} = \ln 2 / \lambda_{z}$ (NOTE: λ _z is the terminal phase rate constant).

NOTES: Additional parameters may be included as required.

8.1.4. BAL Parameters

No pharmacokinetic parameters will be derived for BAL data. The corrected concentrations will be listed, summarised and plotted.

8.1.5. Single Dose Escalation (Part A)

Table 6 Overview of Dose Proportionality Summaries

Endpoint / Parameter/ Display Type	Untransformed						Log-Transformed					
	Stats Analysis			Summary			Stats Analysis			Summary		
	T	F	L	T	F	L	T	F	L	T	F	L
Dose Proportionality												
Dose Proportionality: Power Model								Y				
Dose Proportionality: ANOVA Method								Y	Y			Y

NOTES :

- T = Table, F = Figure, L = Listings, Y = Display generated.
- Stats Analysis = Represents TFL related to any formal statistical analyses (i.e. modelling) conducted.
- Summary = Represents TFL related to any summaries (i.e. descriptive statistics) of the observed raw data.
- Individual = Represents FL related to any displays of individual subject observed raw data.

Boxplots of dose-normalised AUC(0-t), C_{tau} and C_{max} versus dose will be produced, a separate plot for each PK parameter. To calculate the dose normalised parameters, the derived parameter for each dose will be divided by the relevant dose and multiplied by the chosen nominal dose (100ug). If, in the opinion of the Clinical Pharmacology representative, there are a high number of LLQ values at the 100ug dose then another nominal dose will be agreed prior to DBF.

8.1.5.1. Statistical Analysis of Dose Proportionality

The following pharmacokinetic statistical analyses will only be performed if sufficient data are available (i.e. if more than 6 subjects have well defined plasma profiles). If the dose with limited data is at the lower end of the dose range, the data will be excluded and the appropriate analysis conducted on the rest of the data. However if there are non-calculable PK parameter data at intermittent doses no statistical analyses will be performed. A minimum of 3 doses will be required to assess dose proportionality. The assessment of dose proportionality will utilise Part A data only.

Pharmacokinetic Statistical Analyses for Dose Proportionality: Power Method
Endpoint(s)

 AUC(0-t), C_τ, C_{max} Each endpoint to be assessed separately.
Model Specification

 $\log_e(Y) = \beta \times \log_e(\text{dose}) + \log_e(\alpha)$ where Y is the pharmacokinetic parameter and $\log_e(\alpha)$ is an intercept term.
Model Checking & Diagnostics

 Refer to Appendix 8: Model Checking and Diagnostics for Statistical Analyses.
Model Results Presentation

 The coefficient of the slope with 90% confidence intervals, on the log scale, will be calculated, using the pooled estimate of variance, and used to assess dose proportionality. Point estimates and confidence intervals for the slope will be reported to 2 decimal places

The ANOVA method will also be used to assess dose proportionality.

Pharmacokinetic Statistical Analyses for Dose Proportionality: ANOVA Method
Endpoint(s)

 • AUC(0-t), C_τ, C_{max} • Each endpoint to be assessed separately.
Model Specification

 • The PK parameter will be dose-normalised prior to log_e-transformation by multiplying by reference dose / dose • Dose will be fitted as a fixed effect, subject as a random effect using DDFM=KR. • Separate lines will be fitted for each cohort by including terms for cohort and cohort*log_e(dose). If the slopes are not significantly (p-value<0.05) different from each other, the interaction term will be removed and a single slope estimate obtained. If the slopes are significantly different from each other, a separate slope estimate and associated 90% confidence interval will be reported for each cohort. • The reference dose will be chosen based on the lowest clinically relevant dose over which PK can be adequately described, with each other dose as the test doses in the construction of the ratio $\mu(\text{test})/\mu(\text{reference})$.
Model Checking & Diagnostics

 • Refer to Appendix 8: Model Checking and Diagnostics for Statistical Analyses.
Model Results Presentation

 • Point estimates for the adjusted means on the log_e scale, the mean difference between each dose (test) and the reference dose and associated 90% confidence interval will be constructed using the residual variance. These will not be presented. • The point estimate and confidence interval will then be exponentially back-transformed to allow the presentation of the adjusted (least square) geometric means for each treatment (dose), and point estimates and associated 90% confidence intervals for the ratio test/reference. • Point estimates and 90% confidence intervals for AUC, C_{max} and C_τ will be reported to 2 decimal places Treatment ratios and 90% CIs will be plotted by dose. • Plots will also be provided showing the adjusted geometric mean ratio of test to reference treatment (dose) for AUC(0-∞), AUC(0-t), C_τ and C_{max} together with 90% confidence interval.

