10.4. Appendix 4: Data Display Standards & Handling Conventions

10.4.1. Study Treatment & Sub-group Display Descriptors

Treatment Group Descriptions			
RandAll NG		Data Displays for Reporting	
Code	Description	Description ^[2]	Order ^[1]
A	Placebo inhaled single dose	Placebo	1
B	50ug GSK2292767 inhaled single dose	50ug OD	2
C	Dose Level 2 GSK2292767 inhaled single dose	100ug OD	3
D	Dose Level 3 GSK2292767 inhaled single dose	200ug OD	4
E	Dose Level 4 GSK2292767 inhaled single dose	500ug OD	5
F	Dose Level 5 GSK2292767 inhaled single dose	1000ug OD	6
G	Dose Level 6 GSK2292767 inhaled single dose	2000ug OD	7
H	Placebo inhaled repeat dose	Placebo	1
I	Dose Level 7 GSK2292767 inhaled repeat dose	XXXXug OD	2

NOTES:

1. Order represents treatments being presented in TFL, as appropriate.
2. Replace X's with the actual agreed dose for the cohort and period.

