10.11.7. Pharmacokinetic Figures

Pharmacokinetic : Figures					
No.	Population	IDSL / TST ID / Example Shell	Title	Programming Notes	Deliverable [Priority]
Part A (Single Dose Escalation): Pharmacokinetic Concentrations					
3.101	PK (Part A)	PKCF1x	Individual Subject Plasma GSK2292767 Concentration-Time Plots (Linear and Semi-log) by Treatment (Single Dose)	One treatment per page (all subjects within a treatment group on one plot). Add a horizontal line at y-axis = 20 pg/mL and footnote: LLQ = 20 pg/mL, Set pre-dose NQs to missing.	SAC
3.102	PK (Part A)	PKCF3	Median Plasma GSK2292767 Concentration-Time Plot (Linear and Semi-Log, Single Dose)		SAC
Part B (Repeat Dose): Pharmacokinetic Concentrations					
3.201	PK (Part B)	PKCF1	Individual Subject Plasma GSK2292767 Concentration-Time Plots (Linear and Semi-log) by Treatment (Repeat Dose)	If more than one cohort, then 1 cohort per page (all subjects within a treatment group on one plot). Add a horizontal line at y-axis = 20 pg/mL and footnote: LLQ = 20 pg/mL, Set pre-dose NQs to missing.	SAC
3.202	PK (Part B)	PKCF3	Median (+ SD) Plasma GSK2292767 Concentration-Time Plot (Linear and Semi-Log, Repeat Dose)		SAC

Pharmacokinetic : Figures					
No.	Population	IDSL / TST ID / Example Shell	Title	Programming Notes	Deliverable [Priority]
Dose Proportionality					
3.103	PK (Part A)	Fig 3.9 in /arenv/arprod/ gsk2269557/p ii116617/parts _cb/drivers/f_ pkcmax_dose norm_partcb.s as	Box Plot of Dose Normalised Plasma GSK2292767 PK Parameters against Dose (Single Dose)	Separate plots for AUC(0-t), Ctau and Cmax	SAC
3.104	PK (Part A)	Fig 3.10 from /arenv/arprod/ gsk2269557/p ii116617/parts _cb/drivers/f_ pkanova_part cb.sas	Plot of Adjusted Geometric Mean Treatment Ratios and 90% CIs for Plasma GSK2292767 AUC (0-t) to Assess Plasma Dose Proportionality (Single Dose, ANOVA Model)		SAC
Part B (Repeat Dose): Dose Accumulation, Steady State and Peak to Trough Ratios					
3.203	PK (Part B)	Fig 3.11 from /arenv/arprod/ gsk2269557/p ii116617/parts _cb/drivers/f_ pkcmax_boxpl ot_partcb.sas	Box Plots of GSK2292767 Plasma PK Parameters by Day (Repeat Dose)	Exclude mean value. Raw means. Cmax, Ctrough and peak to trough ratio on separate pages	SAC

Pharmacokinetic : Figures					
No.	Population	IDSL / TST ID / Example Shell	Title	Programming Notes	Deliverable [Priority]
Part B (Repeat Dose): Lung ELF and Cell Pellet Data					

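### AUC(0-t) is the only AUC in the dose-proportionality models, so the slope can be biased above 1 if low doses fall below the assay limit earlier than high doses

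*SAP*

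**What the plan says.** SAP section 8.1.5.1 lists the same endpoints for the power model and the ANOVA: "AUC(0-t), C_τ, C_{max"}. Table 5 in section 8.1.3.1 defines AUC(0-t) as the area "from time zero to the time of the last quantifiable concentration". The programming note for Figure 3.101 (section 10.11.7) gives the assay limit: "Add a horizontal line at y-axis = 20 pg/mL and footnote: LLQ = 20 pg/mL". Section 10.4.1 lists six single-dose levels from 50 to 2000 µg, a 40-fold range.

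Two other AUCs, AUC(0-24) and AUC(0-∞), are derived in Table 5, but neither is a listed proportionality endpoint. The ANOVA presentation text nevertheless promises plots of the adjusted "ratio of test to reference treatment (dose) for AUC(0-∞), AUC(0-t), C_τ and C_{max"}. The titles of Tables 3.105 and 3.106 name only Cmax, AUC(0-t) and Ctau, and the title of Figure 3.104 names only AUC(0-t).

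Section 8.1.5.1 contains partial safeguards. The analysis needs more than 6 subjects with well-defined profiles, low-end doses with limited data are left out, and at least 3 doses must remain. The ANOVA reference is the lowest clinically relevant dose whose PK can be adequately described.

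**The concern.** The end of the integration window is set by the assay and not by the design. If exposure is proportional, a higher dose stays above a fixed LLQ for at least as long as a lower one, so its AUC(0-t) covers at least as much of the profile. Whenever the last quantifiable time rises with dose, part of the slope in log AUC(0-t) reflects window length. The same holds for ANOVA ratios against a low reference dose.

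At stake is whether an AUC slope above 1 can be read as more-than-proportional exposure. As planned, it could not be separated from an effect of the assay limit, and choosing another AUC after seeing the data would be post hoc. The AUC(0-∞) plot does not close the gap, because no listed endpoint or display supports it.

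**Working it through.** The SAP states no expected slope, so there is no figure to reproduce.

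**Inputs from the SAP.** Doses 50, 100, 200, 500, 1000 and 2000 µg (10.4.1). Post-dose samples at 5, 30 and 45 min and 1, 2, 3, 4, 6, 8, 12 and 24 h (10.1.1.1). LLQ 20 pg/mL (10.11.7). Linear trapezoids when rising and log trapezoids when falling (Table 5).

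**Assumptions, not in the SAP.** Exactly proportional exposure, peak at 5 min, mono-exponential decline with half-life 2, 4, 6 or 12 h, no noise, and a 50 µg peak of 25 to 200 pg/mL.

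**Direction.** Write concentration as C(t) = dose × g(t). Then AUC(0-t)/dose is the integral of g up to the last quantifiable time. That time cannot fall as dose rises, so AUC(0-t)/dose can only stay level or increase. Any bias is upward.

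**Worked case: 50 µg peak 40 pg/mL, half-life 6 h.** k = ln 2/6 = 0.1155 per h, and time is measured from the 5 min peak.
- 50 µg: C(6 h) = 40 × exp(−0.1155 × 5.917) = 20.2 and C(8 h) = 16.0, so the last time is 6 h. AUC = 40 × 0.0833/2 + (40/0.1155)(1 − 0.505) = 173.1, or 3.46 per µg.
- 100 µg: C(12 h) = 20.2 and C(24 h) = 5.0, so the last time is 12 h. AUC = 521.0, or 5.21 per µg.
- 200 µg: C(24 h) = 10.1, so the last time is again 12 h. AUC = 5.21 per µg.
- 500 µg: C(24 h) = 25.2, so the last time is 24 h. AUC = 3260.6, or 6.52 per µg. The value per µg is the same at 1000 and 2000 µg.

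Least squares of log AUC(0-t) on log dose gives a slope of 1.155 over six doses and 1.091 without 50 µg. The dose-normalised ratio of 2000 µg to 50 µg is 6.52/3.46 = 1.88, and to 100 µg it is 6.52/5.21 = 1.25. The true values are all 1. Integrating every dose to 6 h gives a slope of 1.000.

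**Range over half-lives of 2 to 12 h**

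| Assumed 50 µg peak | Slope, six doses | Slope without 50 µg |
|---|---|---|
| 40 pg/mL | 1.08–1.16 | 1.00–1.09 |
| 100 pg/mL | 1.00–1.07 | 1.00–1.06 |
| 200 pg/mL | 1.00–1.04 | 1.00–1.05 |

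Dropping 50 µg usually lowers the slope. The one exception in this grid is a peak of 200 pg/mL with a 4 h half-life, where it moves from 1.042 to 1.048 because the three lowest doses share a last time of 12 h. The slope is exactly 1.000 where all doses are quantifiable to 24 h, for example at 100 pg/mL with a 12 h half-life.

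**With noise.** Assume 6 subjects per dose, between-subject log SD 0.4, assay log SD 0.15 and 500 replicates. At a 50 µg peak of 60 pg/mL (3 × LLQ) and a 6 h half-life, the mean slope is 1.13 for AUC(0-t), against 1.00 for the untruncated 0–24 h area. At 200 pg/mL the values are 1.05 and 1.00 (rounded).

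**Is AUC(0-∞) a cure?** For mono-exponential profiles, extrapolation is exact by construction. Now assume a bi-exponential decline (70% with a 1 h half-life, 30% terminal), a 50 µg peak of 60 pg/mL, and λz from the last three quantifiable points. With a 6 h terminal half-life, AUC(0-t) gives 1.26 and AUC(0-∞) still gives 1.12. With 12 h the values are 1.27 and 1.18. An area over the common quantifiable interval gives 1.00 in each case.

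**The case against.** The strongest objection is that the SAP does not show truncation will occur. A reader might infer an expectation from the remark in section 8.1.5 about what happens if "there are a high number of LLQ values at the 100ug dose". That sentence is a contingency for choosing the nominal dose of the boxplots, with 100 µg as the default. It shows that LLQ values at a low dose were considered possible, no more. This objection stands, and the bias may be zero.

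The exclusion rule also matters. At a 50 µg peak of 25 pg/mL and half-lives of 4 to 12 h, the six-dose slope is 1.34 to 1.40, but the 50 µg dose then has only 4 to 6 of 11 samples quantifiable and may well be excluded. Without it the slope is 1.11 to 1.17. The larger figures should therefore not be quoted as what the plan would produce. The rule still does not close the gap: AUC(0-t) can be calculated from a short profile, and a well-defined profile is not tied to a last quantifiable time.

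The consequence is limited too. This is a secondary PK estimate with no stated acceptance bounds. Cmax is modelled in parallel and is not shortened by an early last time. Individual plots carry the LLQ line and listings show the λz points (10.4.3), so a careful reader could see truncation. But Cmax measures peak, not total exposure, and section 10.4.3 keeps the extrapolated percentage out of the summary tables.

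**Conclusion.** The concern holds in conditional form. Where the last quantifiable time differs by dose, AUC(0-t) biases the proportionality slope and the ANOVA ratios upward, and the plan models no AUC that guards against this. Under the mono-exponential assumptions above the bias is up to 0.16 on the slope at a 50 µg peak of 40 pg/mL, up to 0.07 at 100 pg/mL and up to 0.04 at 200 pg/mL. It can be larger with bi-exponential decline, and it is nil when all analysed doses are quantifiable to 24 h. All sizes depend on assumed exposure and half-life.

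A reader might conclude that low doses will be truncated and the slope will exceed 1, or that AUC(0-∞) alone would put this right. The SAP gives no concentrations to support the first, and the bi-exponential cases contradict the second. Independently of any assumption, the endpoint lists and the promised AUC(0-∞) plot in section 8.1.5.1 disagree and must be reconciled. This is a cheap improvement to a secondary analysis.

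**What to change.** 1. Add to both models an AUC over a common interval that is quantifiable at all analysed doses, with the rule for choosing the interval fixed before database freeze. Base the AUC proportionality statement on it when the last quantifiable time differs by dose.
2. Add AUC(0-∞) to the endpoint lists as supportive, for profiles with an adequate terminal phase and a pre-set limit on the extrapolated area. Align Tables 3.105 and 3.106 and Figure 3.104 with the list.
3. Keep AUC(0-t) as supportive and show the last quantifiable time by dose.

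The cost is small: the common-interval AUC is one more derived parameter, AUC(0-∞) is already derived, and both enter models already planned. The downsides are that the common interval may be short and so cover only part of total exposure, and that some low-dose profiles will lack a usable AUC(0-∞). Those profiles may be the lower-exposure ones, which is a further reason to keep AUC(0-∞) supportive.
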